## 7.2. Safety Analysis

Descriptive statistics on available patient characteristics (e.g., age, BMI, smoking and alcohol use, history of relevant medical diagnoses, use of relevant concomitant medications) will be reported for all exposure groups at baseline.

Incident cases of study endpoints will be included in the analysis. Women with a history of study outcomes recorded in the medical records prior to the index prescription will not be included in the primary analysis for that specific outcome, but will be analyzed separately. For example, a woman with a history of VTE prior to the index prescription will be categorized as a prevalent case and will be excluded from the primary VTE analysis. A

separate analysis for women with a medical history of VTE will be performed and the woman would remain eligible for the analysis of other outcomes as normal. Depending on the number of patients in these subgroups of prevalent cases of each endpoint, this supplemental analysis is likely to have low power to perform any statistical comparison and will be descriptive in nature.

Incidence rates will be calculated for all endpoints in all treatment groups; incidence rate ratios and 95% confidence intervals will be calculated and compared. Stratifications by risk factors of interest (e.g., age, BMI, history of selected medical comorbidities, selected concomitant medications) will be performed for each outcome depending on availability of the data. A multiple regression model may be fit for the primary objective of the study depending on the completeness of the data on potential confounders and accrual of a sufficient number of endpoints.

A time to event analysis may be conducted as a secondary analysis.

All analyses will be conducted for each country separately, as well as after pooling the data from all participating countries.

Given the rarity of certain malignancies in this population, the incidence rates observed in this study may be small and imprecise. In such case, to better characterize the rates obtained in this study, an additional analysis using external reference data for the malignancies may be conducted. The observed frequency of malignancies in all three treatment groups will be compared with the expected frequency calculated from an age and gender matched population-based reference group (e.g., GloboCan) This ratio of observed versus expected events and 95% confidence interval, will be reported.

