## 10. POTENTIAL WEAKNESSES

**Lack of hospitalization data:** The Cegedim LPD collects data from GP offices. Therefore, complete records of events requiring hospitalization are not available in the database. Since no patient identifiers are available it is also not possible to link to any available national or regional registries to obtain additional information (e.g., vital status, diagnosis of malignancies).

**Data collection in routine care:** The Cegedim LPD collects real life clinical practice information from the actual medical records of the patients. No study specific CRF will be used to collect supplemental information that are not entered in the medical records as part of the patient's routine clinical care. Also, as a non-interventional study, this protocol does not mandate any study specific visits, procedures or laboratory tests.

**Dependence on market uptake of the study medication:** Bazedoxifene is a newly launched product in the participating countries. Since there is no active enrollment of patients (i.e., in contrast to a de novo prospective follow up study), the final sample size will be based on the rate of the uptake of the drug in the participating countries during the subject accrual period.

**Potential for missing data:** The data for this study will come from routine clinical care. No individual patient identifiers will be available. Therefore it is not possible to query the physicians providing the data for any missing information.

**Difference in indication for Bazedoxifene and Raloxifene:** Bazedoxifene is indicated for the treatment of post-menopausal osteoporosis whereas Raloxifene is indicated for both the prevention and treatment of post-menopausal osteoporosis. As a result the characteristics of the cohort of women receiving Raloxifene may differ from the women who are receiving Bazedoxifene. It is possible that the Raloxifene cohort will have a higher proportion of healthier, younger women.

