Patient data collected by Cegedim in each country participating in the LPD varies to some extent to accommodate local needs. However, all countries collect data on medical comorbidities and outcomes, prescriptions, demographics, and physician characteristics.

In the Cegedim electronic medical record system diagnosis of clinical events are recorded as diagnostic codes. These codes from the different participating countries will be harmonized based on pre-specified algorithms developed prior to the analysis and listed in the statistical analytic plan.

Cegedim LPD does not collect hospitalization data directly in Italy and Spain. Information on hospitalizations is captured in the patient's general practice file during follow-up visits with the patient's general practice physician following discharge from the hospital. However, this information is not systematically collected and there is no established linkage between the medical records at the general practices and at the hospitals.

Table 2: Data coding conventions in the different countries

	Italy	Spain
Drug code dictionary	Farmadati	Vademecum
Therapy classification	Anatomical Therapeutic Chemical (ATC)	ATC
Disease classification	ICD-9	Code ICPC mapped to ICD-9

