In the determination of person years, the date of first prescription of treatment will be used as a surrogate for time of first exposure to treatment, since the date when the patient had their first treatment for osteoporosis may not be consistently ascertainable. The same definition of person-time ('ever' exposed approach accounting for all person-times of exposure) will be used for all the study endpoints given that they are all chronic diseases or malignancies with potentially long latency periods. If no primary end point occurs during the follow-up period, the duration will be calculated from the start of treatment date to the last patient visit or the end of study period, whichever comes first.

Both methods of calculating incidence rates will be used and the number of patients for whom the date of first treatment for osteoporosis could not be ascertained will be provided as part of the sensitivity analysis of the incidence density approach.

Stratifications by risks of interest (e.g. age, BMI, or selected medical history) will be performed for each outcome and descriptive summaries will be reported. For example, VTE incidence will be stratified according to age as well as by BMI. Other stratifications by medical co-morbidities and other variables of interest will also be performed as appropriate.

Given the rarity of certain malignancies in this population, the incidence rates observed in this study may be small and imprecise. To better characterize the rates obtained in this study, an additional analysis using external reference data for the malignancies will be conducted, i.e. a standardized incidence ratio (SIR). The observed frequency of malignancies in all three treatment groups will be compared with the expected frequency calculated from an age and gender matched population-based reference group (e.g., GloboCan). This SIR of observed versus expected events and 95% confidence interval, will be reported.

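### The malignancy SIR sets cancers found in GP records against an external population reference with no allowance for under-recording, so a value near or below 1 cannot be read as reassurance.

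*SAP*

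**What the plan says.** SAP 8.1.2 (Incidence Rates) notes that rates of some malignancies may be small and imprecise, and responds that "an additional analysis using external reference data for the malignancies will be conducted". The observed frequency in each of the three treatment groups is to be "compared with the expected frequency calculated from an age and gender matched population-based reference group", with GloboCan as the example. The SIR and its 95% confidence interval are to be reported. Protocol 7.2 describes the same analysis as optional ("an additional analysis using external reference data for the malignancies may be conducted"). Neither text mentions completeness of capture.

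Other sections describe the data behind the observed count:

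- Protocol 10 says that "complete records of events requiring hospitalization are not available in the database". It adds that "it is also not possible to link to any available national or regional registries to obtain additional information", and gives malignancy diagnoses as an example of that information.
- SAP 2.1 says hospital information in Italy and Spain enters the GP file at visits after discharge, but "this information is not systematically collected and there is no established linkage between the medical records" at the practices and those at the hospitals.
- SAP 7 treats any unrecorded condition, other than osteoporosis itself, as absent.
- SAP 2.1 and 8.1.2 end follow-up at the last visit. Deaths are not recorded in either database.
- Protocol 6.3 plans expert review of identified breast, ovarian, renal, thyroid and endometrial cancers. Gastrointestinal and lung cancers are not on that list.
- Protocol 4.1 and SAP 2.1 require only six months of prior record.

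**The concern.** An SIR can be interpreted when cases are found in the same way, or equally completely, on both sides. Here the numerator depends on a hospital diagnosis reaching the GP file, while the denominator comes from a population source that does not depend on GP recording. A cancer that never reaches the GP file counts as no cancer, but the woman's person-time up to her last visit still adds to the expected count.

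The SIR was added for the malignancies where direct rates are weakest, so it will be consulted where other evidence is thin. In a post-authorization safety commitment, a ratio near 1 would naturally be read as no excess over the general population. Under-recording alone could produce that value, and nothing in the SAP warns the reader.

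**Working it through.** **No figure to reproduce.** The documents give no SIR, expected cancer count, reference rate or capture proportion. The values of s, F and E below are assumptions, and the sizes are conditional on them.

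**Formula.** Let s be the proportion of true incident cancers that reach the GP record (relative to the reference source), F the number of false positives and E the expected count. Then

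expected observed SIR = s × true SIR + F/E.

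**Step 1: under-recording alone (F = 0).**

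| True SIR | s = 1.0 | s = 0.9 | s = 0.8 | s = 0.7 | s = 0.6 |
|---|---|---|---|---|---|
| 1.0 | 1.00 | 0.90 | 0.80 | 0.70 | 0.60 |
| 1.3 | 1.30 | 1.17 | 1.04 | 0.91 | 0.78 |
| 1.5 | 1.50 | 1.35 | 1.20 | 1.05 | 0.90 |

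An excess disappears (observed SIR of 1) when s = 1/true SIR: 0.77 for a true SIR of 1.3 and 0.67 for 1.5.

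**Step 2: effect on the confidence interval.** Exact Poisson limits were used. The 95% CI lies above 1 when the count is at least k, the smallest value with P(Poisson(E) ≥ k) ≤ 0.025. This gives k = 30, 54 and 99 for E = 20, 40 and 80. With a true SIR of 1.5 the count is Poisson with mean 1.5 × s × E, and the chance that the CI excludes 1 from above is:

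| E | s = 1.0 | s = 0.9 | s = 0.8 | s = 0.7 |
|---|---|---|---|---|
| 20 | 52% | 31% | 13% | 4% |
| 40 | 80% | 52% | 21% | 4% |
| 80 | 98% | 82% | 39% | 6% |

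As an example with E = 40, 60 cases give an SIR of 1.50 (1.14 to 1.93). At 80% capture, 48 cases give 1.20 (0.88 to 1.59).

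In the other direction, with a true SIR of 1.0 and s = 0.8, the CI lies wholly below 1 in 13%, 22% and 43% of studies for E = 20, 40 and 80. At full capture the figure is about 2%.

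For a single rare site with E = 5, the chance of showing a true SIR of 1.5 is only 14% at full capture and 4% at s = 0.8. There the SIR says little in either case.

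**Step 3: what would cancel the bias.** Missed cases number (1 − s) × true SIR × E, and the bias vanishes when F equals that number. With E = 40, a true SIR of 1.3 and s = 0.8, there are 52 true cases, of which 41.6 are recorded and 10.4 missed. About 10 false positives would bring the SIR back to 1.3. The documents give no basis for estimating F.

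**Step 4: comparisons between cohorts.** If s is the same in two cohorts, it cancels: (s × 1.5)/(s × 1.0) = 1.5 for any s.

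**The case against.** Much of the case on the other side stands.

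- **The net sign is not settled.** A reader might infer that every difference between the two sides lowers the SIR, or that the external SIR is a lower bound. The documents support neither. Excluding women with a prior cancer removes their person-time as well as their cases. Ending time at the last visit limits unobserved person-time and so the expected count. A six-month minimum look-back can let an old cancer be coded as new. False positives among gastrointestinal and lung cancers are not on the list for review and would stay in.
- **The numerator is not stated to be confirmed cases only.** A reader might infer this from Protocol 6.3, but SAP 8.1.2 defines cases as patients with a diagnosis and does not restrict the SIR to reviewed cases.
- **Incomplete cancer capture is an inference.** The documents speak of hospital events and missing linkage, and some hospital information does reach the GP. They call the reference population-based, not complete. The inference is still reasonable, because Protocol 10 itself names malignancy diagnoses as information that linkage could have supplied.
- **The SIR is an additional analysis with no decision rule.** The planned comparisons are hazard ratios within the database, which equal under-recording does not bias. SIRs are also reported for all three cohorts, so a general shortfall would tend to show in the comparators too.
- **Moving from optional to planned is not a fault.** Protocol 7 lets the SAP elaborate and modify the analysis.

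None of this answers the remaining point: the external ratio depends on capture that the protocol lists as a weakness, and the SAP gives no means of interpreting it.

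**Conclusion.** The concern holds in limited form. The planned SIR compares counts ascertained in different ways, and under-recording lowers it in proportion to capture. At an assumed 80% capture with no false positives, a true 1.3 is seen as 1.04. With 40 expected cases (also assumed), the chance of showing a true 1.5 falls from 80% to 21%. These sizes are illustrations, since the documents give neither capture nor expected counts. The net direction is likely downward but not proved.

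The conclusion at risk is narrow: a statement, drawn from the external SIR, that malignancies are no more frequent than in the general population. The comparisons of bazedoxifene with bisphosphonate and raloxifene lose events through under-recording but are not biased by it if it is equal across cohorts. This should be changed, but it does not threaten the primary objective.

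**What to change.** In SAP 8.1.2:

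1. Keep the external SIR, and show it over a stated range of capture, for example 60% to 100%, by multiplying the expected count by s.
2. Add an internal SIR. Take expected counts from women aged 45 or over in the same database who were not prescribed a study drug, by age band, country and calendar year. Apply the same codes, look-back, prior-cancer exclusion and censoring at last visit. Count code-identified cases, without case review, on both sides. These women have no index prescription, so the SAP must also define when their time at risk starts.
3. State that an external SIR near or below 1 will not be taken as evidence of no excess.

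Items 1 and 3 need only wording and simple arithmetic. Item 2 needs one further extraction from a database that sees about 800,000 Italian and 320,000 Spanish patients a year, plus the programming for the reference cohort. Its weakness is that untreated women may differ from treated women in GP contact and baseline cancer risk. The two SIRs should therefore be reported side by side, with neither replacing the other.

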8.1.3 SENSITIVITY ANALYSIS

For each prescription, duration of drug exposure will begin to accrue from the date of the prescription. The duration of drug exposure will be categorized into:

- ***Current exposure:*** defined as the duration of the prescription
- ***Recent exposure:*** defined as the 60-day period following the end of the duration of prescription
- ***Past exposure:*** defined as any follow up time accrued after 60 days following the end of the duration of the prescription.

Given the discontinuous nature of osteoporosis medication use, it is likely that a large number of women in this study will accrue 'current exposure', 'recent exposure' and 'past exposure' exposure time to multiple osteoporosis drugs during the 5-year period of follow up.

A sensitivity analysis will be conducted that compares using a 30-day and a 90-day definition of recent exposure with using the 60-day definition.

Exposure to the drugs under study will be ascertained by searching the prescription records for the relevant product codes. For each prescription the duration of exposure will be estimated based on the dose and quantity of the prescribed medication. For patients that switch treatment, the as-treated (AT) approach will be used in calculating the exposure time (see section below on patients switching treatment for more details).

There will be rules for handling missing values of dose or quantity prescribed in Italian and Spanish LPD databases. In LPD databases, the number of days of supply or daily

dose is not recorded by some GPs in Spain and Italy. If duration is not available, the number of days of supply will be calculated by dividing total number of pills (number of prescribed box times number of pills in a box) by the daily dose. If duration and daily dose are not available, the number of days' supply will be calculated by dividing total number of pills (number of prescribed box multiplied by the number of pills in a box) by the standard dose/recommended dose.

Drug exposure will also be categorized with respect to the cumulative exposure to each drug (e.g., 0-days, 1-30-days, 31-90-days, 91-180-days, 181-365-days, >365-days) to evaluate whether or not the incidence (hazard) of a specific adverse event varies with increased duration of use.

8.1.4 TIME TO EVENT ANALYSIS

A time to event analysis to compare the risk between treatment cohorts, i.e., the BZA, raloxifene and bisphosphonate treated groups, will be conducted for the primary end point (VTE) and other secondary endpoints if sufficient data are available,

[figure not shown]
The time to an event will be calculated as the time from index prescription date to the incidence date of primary end points. If a patient does not have a primary end point, the treatment duration will be based upon the index prescription date to the last visit or end of follow-up period, whichever comes first.

In order to ensure the exact duration from the start of treatment to the incidence of primary endpoints, a subgroup of newly prescribed patients who were diagnosed with osteoporosis during the enrolment period will be used first.

In the very unlikely event that the number of bisphosphonate or raloxifene patients are less than the number of BZA patients, the analysis will be extended to include bisphosphonate and raloxifene patients whose treatment began prior to the enrolment period. Considering the fact that bisphosphonates and raloxifene were launched before BZA (See the figure below), some patients could have already gotten treatment of bisphosphonates and raloxifene prior to the enrolment period (i.e., before BZA was launched). For such patients the start date will be the first date of treatment for bisphosphonates or raloxifene, available within the database.

Figure 1. Calculation of duration (from start date to the incidence of primary endpoint) for the treatment cohorts

The time to event analysis model will also be used to test for differences in time to event while adjusting for covariates of interest.

This model will take into account the duration to the incidence of the endpoint and control for imbalances in outcome risk factors, as determined based on the baseline descriptive analysis.

The following factors possibly related to the incidence of the primary end point will be considered.

- Treatment group (BZA, raloxifene, and bisphosphonate)
- Age
- BMI
- Reported history of smoking (If the reported frequency of smoking status is low this will be excluded)
- Reported Medical History of Diabetes, Hypertension, Malignancies
- Time since diagnosis of osteoporosis
- Previous treatment for osteoporosis (before index date) or Number of different treatments for osteoporosis in the entire patient history available
- History of DVT or PE
- Previous history of major lower extremity (hip, knee) arthroplasty, arthroscopic surgery (information on arthroscopic surgery not available in Italian database)
- General surgery, major orthopedic surgery (<1month prior to incidence of VTE)
- (Information on general surgery not available in Italian database)
- Multiple trauma (<1month prior to incidence of VTE)
- Hip, pelvis, or leg fracture (<1month prior to incidence of VTE)
- Stroke (<1month prior to incidence of VTE)
- Acute spinal cord injury (paralysis) (<1month prior to incidence of VTE)
- Hormone replacement therapy (limited information available in both databases)

A Cox model will be used in order to take into account the time varying component. The time from the beginning of the treatment (one among three types, BZA, raloxifene, and bisphosphonate) to the occurrence of primary end point is fitted in this model. The Proportional Hazards (PH) assumption will be tested for each covariable. If the PH assumption does not hold for some covariates, the use of time-varying HR for those covariates will be explored. If a categorical variable with more than 2 levels does not satisfy this PH assumption, collapsing some categories will be attempted to satisfy the PH assumption. Correlations between variables will also be evaluated in order to find independent factors and a final model that is clinically relevant.

First, the univariate analysis will be carried out on each covariable in order to determine the explanatory variables to be included in the final multivariate model. All significant variables with a p -value ≤ 0.20 in the univariate model will be taken into account in the multivariate Cox model.

If > 80% of the important risk factors for VTE listed above does not satisfy the PH assumption, a logistic regression analysis would be performed instead of Cox model to otherwise determine if the covariable is related to the incidence primary endpoint (VTE). The dependent variable would be the incidence of the primary end point during the follow-up period categorized as a binary variable. The 2 indicators of treatment group (BZA vs. bisphosphonates, raloxifene, will be forced in the multivariate model (Cox model or logistic model) to analyze incidence in each class of treatment, adjusted on

significant factors. Hazard ratios (HR) (odds ratios (OR) in case of logistic regression) with 95% Confidence intervals (CIs) and p-values will be presented.

[figure not shown]
Patients Switching Medications

In the treatment of chronic conditions such as osteoporosis, patients may discontinue their study medication (BZA/bisphosphonate/raloxifene) or change study medications. Such exposure changes are often due to treatment failure or perceived/real side effects. The stronger such non-adherence is associated with the outcome; the more an as-treated (AT) analysis, which censors at the point of discontinuation, will be biased. A cumulative risk (CR) (similar to intention-to-treat analyses in randomized trials) analysis follows all patients for a fixed time period, carrying forward the initial exposure status and disregarding any changes in treatment status over time. Because this analysis disregards informative non-adherence, it will not suffer bias as a consequence of censoring, but it will suffer bias as a consequence of exposure misclassification. Such misclassification increases with a longer follow-up period and a shorter average time to discontinuation. In most cases, though not all, such misclassification will bias effects towards the null, similar to intention-to-treat analyses in randomized trials. Viewed separately, the AT and CR analyses trade biases, but together they give a range of plausible effect estimates. Adjusting for non-adherence in an analysis of a drug effect requires information about the predictors of treatment discontinuation, which is not available with sufficient accuracy in secondary data such as that used in this study [1].

In this study the proportion and demographic and clinical characteristics of patients that switch medications between the study drugs will be reported alongside patients that do not switch medications. Both the AT and CR analytic approaches will be used for all study endpoints and the results reported. In the CR method, if a patient switches from one exposure (study drug) cohort group to another, they will have several treatment durations and will belong to multiple cohort groups but will be analyzed according to their original exposure cohort group (i.e., CR/intent to treat approach). In the AT approach, all exposure cohort groups will be included as a time-dependent variable. With the exposure cohort group as a time-dependent variable, each event will be assigned to the treatment being taken at the time of occurrence. The duration of treatment for each cohort group will be from the date of the first prescription to the date of the event or to the end of treatment, whichever occurs first. The covariates of patients that switched treatment at the time of the event or at the end of follow-up would be considered in this model.

[figure not shown]
The following diagrams shows some example of calculating duration for patients with switched treatments with both the AT and CR approaches.

Figure 2a. Calculating the duration of treatment for patients that switched treatment using the as-treated (AT) approach.

A, B, C: Treatment cohort types. X= Incidence date of primary end point

Figure 2b. Calculating the duration of treatment for patients that switched treatments using the cumulative risk (CR) approach.

A, B, C: Treatment cohort types. X= Incidence date of primary end point

